To achieve these aims, we will recruit and randomize 40 BIPOC trans women, aged ≥ 18 years, to intervention or a waitlist control for 12 weeks (e.g., 20 trans women per arm). Participants will complete baseline, end of program, and 3-month follow-up surveys. Immediately following the intervention program end, participants will also complete a qualitative exit interview regarding their experience. The specific feasibility benchmarks are to a) achieve a recruitment rate of at least 5-6 participants per month; b) maintain a retention rate of 70% or higher; and c) obtain estimates of outcomes (less than 10% missing data) and ensure measures and data collection are suitable to explore if participants who receive the intervention will report increased HIV prevention and care outcomes post-intervention compared to those in the control condition. We will also gather information from participants during exit interviews and interviews with key stakeholders and staff delivering the intervention to identify strategies for sustainability with BIPOC trans women in US-based settings, and we will use these data and input from our community advisory board (CAB) to refine the intervention for a future efficacy trial.

The proposed study has the potential for high public health impact by evaluating the feasibility and acceptability of a community-centered microeconomic intervention. Our focus on BIPOC trans women is in line with the prioritization of sexual and gender minority communities for health disparities research,^{31,32} and NIH funding priorities to address social-structural drivers of inequities in both the HIV prevention and care continuum.²⁵ Study findings will provide the necessary groundwork to examine intervention efficacy and implementation processes in a future, large-scale trial.

III. Background Information

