Trans women represent one of the populations at highest risk for HIV infection.³³ Approximately 19-21% of trans women in the US are living with HIV. 14-16 Evidence suggests substantial racial/ethnic inequities in HIV with Black, Latina, and other trans women of color representing the majority of the cases among trans women. 17,18,34 The HIV Prevention and Care Continuum frameworks emphasize the need for reducing HIV transmission and acquisition risk via consistent condom use, regular HIV testing, pre-exposure prophylaxis (PrEP) among HIVnegative individuals, and engagement and retention in HIV care in addition to uptake, adherence, and persistence to antiretroviral therapy (ART) to achieve virologic control among persons living with HIV. 35-37 There are notable inequities in HIV prevention and care continua outcomes among BIPOC trans women.^{38,39} For example, evidence suggests that BIPOC trans women have a 40% lower odds of lifetime HIV testing and 50% lower odds of HIV testing in the past 12 months compared with gay/bisexual men.⁴⁰ Studies also indicate very low PrEP uptake (3 to 32% use among PrEP-eligible trans women), 41,42 and low rates of virologic control (68 to 70%) among trans women living with HIV. 38,43-52 Thus, interventions are needed that address inequities across both the HIV prevention and care continuum among BIPOC trans women in the US.38,51,52

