In line with recommendations by NIH and the research methods literature, given the sample size and intent of the pilot study we will not conduct a formal test of outcomes or attempt to obtain an estimate of effect size. $^{123-136}$ We will consider engagement in HIV prevention and care as an exploratory outcome defined as PrEP use and \geq 80% adherence among those not living with HIV and suppressed HIV viral load among those living with HIV, collected via self-report. These analyses will be conducted as a feasibility check to ensure all measures required to construct the primary outcome and that moderators and mediators for a larger formal RCT are present and will yield analyzable data.

VI-4. Analytical Design

VI-4.1 Acceptability & Feasibility analyses. The principal analytical aim of the pilot RCT is to measure feasibility and acceptability and evaluate whether feasibility and acceptability benchmarks are met. To fulfill this objective, frequency tables for all variables and measures of central tendency and variability for continuous variables will characterize the sample and quantify the intervention feasibility and acceptability outcomes. We will address incomplete data via direct maximum likelihood estimation (MLE) or multiple imputation (MI)¹⁵⁰ assuming that incomplete data arise from a conditionally random (MAR) mechanism¹⁵¹ and include sensitivity analyses to evaluate the robustness of the MAR assumption. The proposed analyses will be conducted using validated algorithms in the general purpose statistical programs SAS or Stata. All statistical software programming code will be fully documented to enable future code review, transparency, and results reproducibility.

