VII-4.2 Baseline Survey: After consenting to participate, potential participants will be asked to complete an online Qualtrics programmed baseline survey. (See "Baseline Survey" Appendix.) The survey should take approximately 40 minutes to complete and will be connected to their assigned Study ID. If they are in-person with the study team member at Ruth Ellis, they may complete the survey on the study team laptop or tablet; if remote they will be sent a link via email and/or text message to complete on their personal device. If a participant requests to complete the survey at another time during an in-person study visit or exits out of the survey remotely before completion, study team members will attempt contact via phone call, email, or text to remind about completing the survey and provide their unique Qualtrics survey link if they are no longer able to locate it. In order to receive their incentive, at the end of the Qualtrics survey, participants will be asked to provide their name, mailing address, email address, and social security number (required for incentive reconciliation for tax purposes due to the amount of funds provided over the study period). An IRB approved study team member will securely store participants' social security number in a restricted Dropbox folder. (For specific incentive amount, see Section VII-8. Participant Incentives and Other Funds Provided.)

VII-4.4 Randomization: After all previous enrollment activities are completed, participants will be randomized in a 1:1 ratio into *Secure* intervention or the TSoCP/Fair Michigan standard of care waitlist control condition using a computerized secure and fraud-resistant procedure used in our team's prior studies. Assignment will occur until there is sufficient enrollment to form a group. A member of the study team will contact the participant to them know whether they are in the immediate intervention arm or the waitlist control arm. (See "Randomization Survey" Appendix.)

VII-5. Intervention Arm Procedures

During the approximately 12-week intervention period, participants who are randomized to the intervention arm will receive the Secure program components (in-person group sessions, individual mentorship, microgrant funds, and weekly job announcements), in addition to standard of care services (one-time emergency assistance funds, referral to legal gender affirmation services), as described below.

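### The exploratory GLMM states no HIV-status term, although the composite's background rates differ by 36 to 67 points between participants living and not living with HIV

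*Combined protocol and SAP*

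**What the plan says.** All references are to the combined protocol and SAP.

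- **Allocation (VII-4.4).** "After all previous enrollment activities are completed, participants will be randomized" 1:1, "using a computerized secure and fraud-resistant procedure used in our team's prior studies". No stratification factor, block scheme or minimisation is named. The section points to a Randomization Survey appendix that is not part of the available text.
- **Size (Specific Aims).** "we will recruit and randomize 40 BIPOC trans women", given as "20 trans women per arm".
- **Population (IX-2.3).** People who are HIV-negative, of unknown status, or living with HIV can all enrol.
- **Outcome (VI-3).** The exploratory composite is PrEP use with at least 80% adherence "among those not living with HIV and suppressed HIV viral load among those living with HIV", by self-report.
- **Background rates (III).** The plan cites "very low PrEP uptake (3 to 32% use among PrEP-eligible trans women" and, for trans women living with HIV, "low rates of virologic control (68 to 70" percent.
- **Analysis (VI-4.2).** Arm proportions are plotted across the surveys. A GLMM at alpha 0.05 then compares the arms averaged over the post-baseline surveys. Neither HIV status nor the baseline outcome is stated as a covariate.
- **Standing of this comparison (VI-3, VI-4.1, VI-4.2).** Feasibility and acceptability are primary. The outcome comparison is exploratory, and hypothesis testing is played down.
- **Trial status (XI-4).** Enrolment is finished, and all participants have completed the baseline and follow-up surveys.

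**The concern.** What counts as success depends on HIV status, and the plan's own figures make success much more common in one status group than in the other. Two arms with no intervention effect but a different mix of HIV status will therefore show different composite proportions. As written, neither the allocation nor the model deals with that mix. A participant-level random effect does not help, because arm is itself a between-participant factor.

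At stake is how one small realised comparison is read. VI-4.2 wants a preliminary signal, and the pilot is meant to lay the ground for a larger trial. An uneven serostatus split could add to that signal or mask it. A reader who sees only the pooled post-baseline estimate could not tell which had happened.

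**Working it through.** **The plan's own figures.** The documents give no figure for imbalance by HIV status. The nearest stated numbers are in VI-4.3:

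- The interval width of 29.8% for an 80% proportion with N=32 reproduces as an exact (Clopper-Pearson) 95% interval: 62.1% to 92.0%.
- The minimum detectable increase of 33.7% to 42.8% cannot be tied down, because the control rate and within-person correlation are not given. Assuming 16 per arm, two post-baseline surveys, a 17% control rate and correlation 0.1 to 0.7, it comes to 34.1-43.1%, so the stated range is plausible.

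**Inputs.** N=40 and 20 per arm are from the Specific Aims. The share living with HIV is 19-21% (Background), so about 0.20 x 40 = 8; applying this national figure to the sample is an assumption. The rates are 3-32% and 68-70% (Background).

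**Gap between status groups.** Smallest: 68 - 32 = 36 points. Largest: 70 - 3 = 67 points. The 3-32% is PrEP use without the adherence requirement, so the true gap could be wider.

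**Shift under no effect.** Shift = (difference between arms in the share living with HIV) x (gap). With 8 of 40 living with HIV and fixed arms of 20, the split is hypergeometric:

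| Split | Probability, either direction | Share difference | Shift, 36-point gap | Shift, 67-point gap |
|---|---|---|---|---|
| 4:4 | 30.5% | 0 | 0 | 0 |
| 5:3 | 46.0% | 2/20 = 0.10 | 3.6 | 6.7 |
| 6:2 | 19.2% | 4/20 = 0.20 | 7.2 | 13.4 |
| 7:1 | 4.0% | 6/20 = 0.30 | 10.8 | 20.1 |
| 8:0 | 0.3% | 8/20 = 0.40 | 14.4 | 26.8 |

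- P(6:2 or worse) = 2 x (0.0958 + 0.0202 + 0.0016) = 23.5%.
- Mean absolute share difference = 0.098, so the mean absolute shift is 0.098 x 36 = 3.5 to 0.098 x 67 = 6.5 points.
- SD of the share difference = 0.128, so the SD of the shift is 4.6 to 8.6 points.

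**Sensitivity.** With 7 to 16 of 40 living with HIV, the SD of the shift runs from 4.4-8.2 to 5.6-10.5 points, and the chance of a share difference of at least 20 points is 9-33%. With 32 followed up, 6 to 8 of them living with HIV, the SD is 5.0-10.4 points.

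**What adjustment buys.** At one time point with 20 per arm, on the proportion scale:

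- Rates 68%/32%: the pooled rate is 0.2 x 0.68 + 0.8 x 0.32 = 0.392, and the SE is sqrt(2 x 0.392 x 0.608 / 20) = 15.4 points. The within-status variance is 0.2 x 0.68 x 0.32 + 0.8 x 0.32 x 0.68 = 0.2176, and the SE becomes sqrt(2 x 0.2176 / 20) = 14.8 points.
- Rates 70%/3%: the pooled rate is 0.164 and the SE 11.7 points. The within-status variance is 0.2 x 0.70 x 0.30 + 0.8 x 0.03 x 0.97 = 0.0653, and the SE becomes 8.1 points.

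These gains are on the proportion scale. In a logistic GLMM the adjusted log odds ratio need not have a smaller standard error, because it estimates a different, conditional quantity.

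**The case against.** Several stronger readings are tempting, and the documents do not support them.

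- **That allocation was unstratified or simple.** VII-4.4 is silent, and both the prior-study procedure and the appendix are unseen. Only the statement that no stratum is stated can be defended.
- **That this is bias, or that 7-13 points is typical.** It is chance variation already contained in the unadjusted standard error. The typical shift is 3.5-6.5 points, against a standard error of 11.7-15.4 points and a stated detectable increase of 33.7-42.8 points.
- **That the plan's main display is distorted.** The principal analysis is descriptive tables for feasibility and acceptability. The plot serves a secondary goal and includes the baseline survey, so a serostatus imbalance would largely show there as a gap present before the intervention began. That protection does not reach the GLMM, which uses post-baseline proportions only.
- **That VII-4.4 should be rewritten.** With enrolment complete, that would change nothing in this trial.

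There are also fair practical objections. Participants may decline any question (IX-4.2), so status may be missing. With about 4 people living with HIV per arm, plots by status would be unstable and could disclose individuals, against the aggregate-only rule in VIII-2. The rates and the HIV share are literature figures, not sample data.

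All of this stands and limits the point. None of it explains why the strongest known predictor of the composite is absent from the stated model, when the outcome cannot be constructed without knowing status.

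**Conclusion.** The point holds as a modest improvement to a secondary analysis. VI-4.2 should account for HIV status and, as stated, does not. Chance imbalance is worth 3.5-6.5 points on average and 7-13 points at a 6:2 split, with 6:2 or worse about one time in four. These sizes assume 8 of 40 living with HIV, exactly 20 per arm, and the Background rates applying to this sample. A reader might infer a flawed randomisation or a biased trial; the text supports neither. The recruitment, retention and missing-data benchmarks and the acceptability measures do not depend on this comparison.

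**What to change.** In VI-4.2:

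1. Add baseline self-reported HIV status as a fixed effect in the GLMM, coded as living with HIV versus not living with HIV or unknown. State a rule for participants who decline to answer.
2. Report counts by arm and status at baseline alongside the plotted proportions. Give status-specific proportions only where cell sizes allow it without disclosure risk.

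Leave VII-4.4 as it is for this trial. Carry blocked randomisation stratified by HIV status into the future efficacy trial. At this pilot's size, a residual imbalance of one person would move the comparison by at most 1/20 x 36 = 1.8 to 1/20 x 67 = 3.4 points.

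No new data are needed, since the composite already requires status. The cost is one extra term in a small sample. At the low end of the PrEP range, 32 x 0.03 gives about one expected success per survey among those not living with HIV, so the plan should say what is done if the model does not converge. The odds ratio also becomes conditional on HIV status and is not directly comparable with an unadjusted one.
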